#### 4. Background and Rationale:

The well-accepted goals for the anaesthetic management of patients undergoing neurosurgical procedures include the delivery of smooth and hemodynamically stable anaesthesia with provision of good operating conditions and a smooth but rapid emergence that allows for early neurological assessment.(1)

Muscle relaxation is considered as elements of general anaesthesia. Neuromuscular blocking agents (NMBAs) are usually administered during anaesthesia to facilitate endotracheal intubation and/or to improve surgical conditions.

The use of NMDs for general anaesthesia may cause many side effects, which cannot be ignored, such as residual paralysis, delayed recovery from general anaesthesia, recurarization, anaphylactic or anaphylactoid reactions, histamine release, all of which need to be reversed. At last but not least it interferes with the neurophysiologic

monitoring of these patients. (2)

Now we can use nerve stimulator device for easily monitoring of administration of and recovery from neuromuscular blocking agents (NMBAs) whenever possible is recommended.

We agree with the guidelines issued by the Association of Anaesthetists of Great Britain and Ireland (AAGBI) statements that a peripheral nerve stimulator is mandatory when NMBAs are used (3).

Intraoperative neurophysiological monitoring has been established as one of the paths by which modern neurosurgery can improve surgical results while minimizing morbidity. This proceeding consists of the monitoring of functional integrity of the neural pathways and mapping of techniques for identification and preservation of the cranial nerves, their motor nuclei, and corticospinal or corticobulbar pathways during posterior-fossa and brainstem surgery.(4)

During these surgical procedures, small injuries can produce significant neurological deficits, and therefore global integrity of the brainstem must be monitored through transcranial electric motor-evoked potentials (TceMEPs). (5,6)

Preservation of facial nerve (FN) function is a well-recognized goal of tumor excision at the cerebellopontine angle (CPA). Especially in cases of vestibular schwannoma excision, postoperative facial paresis and paralysis may occur despite efforts to avoid injury and maintain anatomic integrity of the nerve during dissection.(9)

Motor-evoked potential monitoring of the FN using transcranial stimulation of the motor cortex (TceMEP) yields information regarding the full facial nerve pathway without requiring direct nerve stimulation.(9)

Direct electrical stimulation can be used intermittently to assist with identification and mapping of the facial nerve location during tumor resection. However, This method can be of limited utility when the nerve course and/or its emergence from the brainstem is inaccessible or obscured by tumor bulk at the CPA.(9)

Current standard of anesthesia in Motor Evoked Potential (MEP) monitored neurosurgeries is TIVA (total intravenous anaesthesia) without muscle relaxant or with shallow NMB because deep NMB prevents monitoring of MEPs during surgery.

To the best of our knowledge, there are no direct comparative studies involving partial versus no neuromuscular blocker effect in facial nerve monitoring of TceMEPs during the surgery of brainstem lesions but rarely there is studies which compare the effect of muscle relaxant in brain tumors ,cerebral aneurysm and spinal surgeries(4).

The use of TceMEP monitoring during surgery for intraparenchymal and extraparenchymal brainstem lesions has become a safe, reliable, and sensitive method to detect and reduce injury to the brainstem, allowing an early intervention to avoid permanent impairment(7).

The effects of muscle relaxation on TceMEPs are an important consideration in intraoperative neurological monitoring during surgery for intraparenchymal and extraparenchymal brainstem lesions for easily and early detection (8).

## **5. Objectives:**

This study is designed to compare the operating condition of two different levels of muscle relaxation on facial nerve monitoring using transcranial motor evoked potential in CPA surgery at KasrAlainy University Hospitals.

- To Estimate End to start facial nerve MEP amplitude ratio
- To determine the effect of neuromuscular relaxant degrees on recovery and hemodynamics.
- To compare doses of hypnotics given at different level of muscle relaxant.
- Assessment of propofol doses needed for enhancement of early recovery and ambulation.

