## **8. Study Methods**

### **Population of study & disease condition:**

40 Patients aged from 18-60 years old, scheduled for Cerebellopontine angle surgery will be included in the study. Patients will be randomly allocated using concealed closed envelope method into one of two groups: Induction will be accomplished with fentanyl, propofol, and a single dose of a neuromuscular blockade. Following intubation, general anesthesia was maintained with a continuous infusion of propofol and fentanyl.

Group A (n=20): will receive Rocronium as muscle relaxant, maintain partial NMB T2\TC 0.5 or TOF count 2 (10) and targeting BIS = (40-60)

Group B (n=20): will not receive muscle relaxant, targeting BIS = 25-35 after ending of monitoring of neurophysiology propofol dose will be dropped to 4–6 mg\kg\hr. targeting Bispectral index 40- 60.

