### **Methodology in details :**

Before induction of anaesthesia and Before Rocronium administration, the baseline twitch response will be established with a neuromuscular nerve stimulator (NMT mechanosensor, GE healthcare, Helsinki, Finland) to achieve the maximum response of the adductor pollicise muscle.

The maximum electromyography amplitude of T1 before Rocronium administration will be considered to be the control response (Tc). The response of the adductor pollicise brevis muscle to TOF stimulation of the ulnar nerve will be monitored every 5 min and will be recorded every 30 min, and the infusion dose of Rocronium will be adjusted according to the target of the partial NMB group.

Anaesthesia will be induced by I.V. propofol (1.5-2 mg/kg) with fentanyl (2–4 mcg/kg) through syringe infusion pump. After induction, tracheal intubation will be facilitated with Rocronium (0.6 mg/kg).

Anaesthesia will be maintained by propofol and fentanyl infusions through the pump. Subjects will be randomly allocated into one of the two groups:

Group A (n=20): will receive Rocronium as muscle relaxant, maintain partial NMB T2/TC 0.5 or TOF count 2 (10) , Fentanyl will be infused at a dose range of 0.5–1mcg/kg/hr. to control the haemodynamic response to the surgical procedure within a 20% range of its preoperative value, and propofol will be infused at a dose range of 6–8 mg/kg/hr. to targeting Bispectral index at 40 -60.(11)

Group B (n=20): will not receive muscle relaxant, Fentanyl will be infused at a dose range of 0.5–1mcg/kg/hr. to control the haemodynamic response to the surgical procedure within a 20% range of its preoperative value, and

propofol will be infused at a dose range of 8–12 mg/kg/hr. to targeting Bispectral index at 25-35, after ending of monitoring of neurophysiology propofol dose will be dropped to 4–6 mg/kg/hr. targeting Bispectral index 40- 60.(11)

The mean arterial pressure during the surgery will be monitored every 5 min and will be recorded every 30 min and will be compared between the groups. Hypotension will be defined as a decrease in the mean arterial pressure of more than 20% of the preoperative value or below 55 mm Hg and will be treated by repeated 5 mg I.V. ephedrine bolus doses. Vasopressor infusion (norepinephrine in starting dose of 0.3 up to 2 mcg/kg/min) will be given if three or more ephedrine bolus doses is required. If bradycardia (60 beats min) developed, 0.6 mg of atropine will be administered.

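### Relaxation level and hypnotic depth are assigned together, so the trial can compare two regimens but cannot attribute differences to relaxation level, as its objectives do

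*Combined protocol and SAP*

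**What the plan says.** Section 5 gives the overall purpose as a comparison of "two different levels of muscle relaxation on facial nerve monitoring using transcranial motor evoked potential in CPA surgery". Four listed objectives follow:

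- The first is neutral: to estimate the end-to-start MEP ratio, which is also the primary outcome.
- The second is "To determine the effect of neuromuscular relaxant degrees on recovery and hemodynamics".
- The third is "To compare doses of hypnotics given at different level of muscle relaxant".
- The fourth is "Assessment of propofol doses needed for enhancement of early recovery and ambulation".

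Section 4 describes the gap in knowledge in the same single-factor terms: "there are no direct comparative studies involving partial versus no neuromuscular blocker effect in facial nerve monitoring of TceMEPs".

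The arms are defined in section 8, in the population paragraph and under Methodology in details. In Group A, which is kept at partial block with a BIS target of 40–60, "propofol will be infused at a dose range of 6–8 mg/kg/hr"; no later change is stated. The population paragraph says Group B "will not receive muscle relaxant, targeting BIS = 25-35 after ending of monitoring of neurophysiology", which runs two statements together. Methodology in details separates them: BIS 25–35 with propofol 8–12 mg/kg/hr applies until monitoring ends, and then propofol falls to 4–6 mg/kg/hr with BIS 40–60. Both groups have the same intubating dose of rocuronium, the same fentanyl range and the same extubation criteria.

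The start MEP is taken before the intubating relaxant and the end MEP at dural closure (Methodology in details). Under Statistical analysis, two groups are compared by an unpaired t test.

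**The concern.** The objectives promise an answer about one factor, and the arms differ in two. Under the objectives as worded, a difference would be reported as an effect of the relaxant, although hypnotic depth could explain part or all of it. Depth could also offset a real effect of the relaxant, and a null result would then be misread. A team that changed only the relaxant and kept BIS at 40–60 could not expect this trial's result, because no arm tests that change.

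Total propofol raises a further difficulty. It is a secondary outcome, and the third objective labels the groups by relaxation level, yet the dose ranges and BIS targets that shape it are themselves assigned.

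**Working it through.** The plan gives no figure for this point. The check sets the arms beside the objectives.

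**1. What is assigned** (section 8)

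| | Group A | Group B, during monitoring | Group B, after monitoring |
|---|---|---|---|
| Relaxant in maintenance | partial block | none | none |
| BIS target | 40–60 | 25–35 | 40–60 |
| Propofol, mg/kg/hr | 6–8 | 8–12 | 4–6 |

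During monitoring, no arm combines partial block with BIS 25–35, or no relaxant with BIS 40–60.

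**2. What two arms can identify.** Write the group difference as D = R + H, where R is the effect of relaxation level and H that of depth (any interaction would be a further unknown). Two arms estimate D only. Adjusting for BIS does not help, because depth is set by group.

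As an illustration, the sample size section plans a 50% fall from 0.72, so D = 0.50 × 0.72 = 0.36. The shares below are assumptions, since the documents give none:

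- H is 0% of D: R = 0.36.
- H is 50% of D: R = 0.36 − 0.18 = 0.18.
- H is 100% of D: R = 0.

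All three give the same expected data and the same t test. If instead R = 0.36 and depth acted against it by 0.18, D would be 0.36 − 0.18 = 0.18.

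**3. Gap in BIS targets during monitoring**

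- Smallest: 40 − 35 = 5 points.
- Midpoints: (40 + 60)/2 − (25 + 35)/2 = 50 − 30 = 20 points.
- Largest: 60 − 25 = 35 points.

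The target ranges do not overlap.

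**4. Propofol rates at the midpoints of the ranges**

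- During monitoring: B (8 + 12)/2 = 10, A (6 + 8)/2 = 7, ratio 10/7 = 1.43. The ranges meet only at 8.
- After step-down: B (4 + 6)/2 = 5, A still 7, ratio 5/7 = 0.71. The ranges meet only at 6.

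Let T1 be the hours of maintenance during monitoring and T2 the hours after it. At the midpoints, B minus A is (10 − 7)T1 + (5 − 7)T2 = 3·T1 − 2·T2, which is zero when T2 = 1.5·T1. The plan gives neither duration, so it does not fix the sign.

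**5. Where depth enters the primary ratio.** The start value precedes the maintenance regimens, so the groups have not yet diverged. The end value is itself a neurophysiological recording, and Group B's step-down follows the end of monitoring. On a plain reading the BIS targets still differ at dural closure, although the step-down time is not stated. Any depth effect is then in the end value only and does not cancel in the ratio.

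**6. Whether depth at the end MEP will be known.** Measurement tools, item 2, has BIS watched every 5 min but, apart from named early points and one after extubation, recorded only every 30 min. No record is tied to the end MEP.

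**The case against.** The strongest reply is that this is a matter of wording. Both arms are fully described in section 8, the randomised comparison is sound, and the objective that matches the primary outcome is neutral. Deeper hypnosis until monitoring ends can also be read as part of a no-relaxant technique, and dropping the deeper target afterwards fits that reading. Much of this stands. Comparing two regimens is a legitimate question. But the protocol never says that this is the question, and describing the arms in the methods does not correct objectives that name relaxation level alone.

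The recovery comparison is partly protected, since both groups finish with the same BIS target and share extubation criteria. That lessens the problem without removing it: Group B has had the deeper exposure, followed by the lower late infusion rate.

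Some stronger inferences are tempting, and the documents do not support them:

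- *That Group B must receive more propofol overall and wake later.* The 1.43 ratio covers the monitoring phase only, and the later ratio of 0.71 runs the other way.
- *That the fourth objective claims a propofol requirement caused by relaxation level.* Read in full, it does not mention relaxation. It still needs rewording, because it treats doses that are partly assigned as doses needed.
- *That a recorded BIS value will always lie within 15 min of the end MEP, half the 30-min interval.* This fails if no record follows dural closure. If closure came 20 min after the last intraoperative record, the gap would be 20 min.

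**Conclusion.** The point holds as one of attribution. The trial can support conclusions about partial block with BIS 40–60 against no maintenance relaxant with BIS 25–35 until neurophysiology ends, then BIS 40–60. It cannot support conclusions about relaxation level for the MEP ratio, recovery, haemodynamics or propofol. The separation during monitoring is 5 to 35 BIS points and, at the midpoints, a propofol ratio of 1.43.

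These are gaps between targets, not achieved depths or effects on outcomes. The size and direction of any depth effect cannot be computed from the documents. For the primary outcome, the conclusion that the targets still differ at dural closure rests on the plain reading that Group B's step-down comes after the end MEP.

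A reader might infer that the comparison is invalid, or that the trial needs a common BIS target or a 2×2 factorial design. Neither follows. The unpaired t test is valid for the two regimens, and a redesign would be needed only if the sponsor wants the effect of relaxation level itself.

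**What to change.** **Section 5**

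- Lead objective: *To compare two anaesthetic regimens for transcranial MEP monitoring of the facial nerve during CPA surgery: partial block with BIS 40–60, and no maintenance relaxant with BIS 25–35 until neurophysiology ends, then BIS 40–60.*
- Second objective: *To compare recovery and haemodynamics between the two regimens.*
- Third objective: *To compare hypnotic doses under the two regimens.*
- Fourth objective: *To describe propofol doses given and early recovery under the two regimens.*

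**Statistical analysis.** Add: *Differences in primary and secondary outcomes are interpreted as effects of the regimen, not of relaxation level alone. A difference in total propofol partly reflects the assigned dose ranges and BIS targets.* Total propofol stays as a tested secondary outcome.

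**Measurement tools, item 2.** Add *and at the end MEP recording*, and report that BIS value by group.

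The cost is four reworded statements, two added sentences and one BIS value per patient (1 × 40 = 40) from a monitor already in use. Treatment, tests, outcomes and sample size do not change. The downside is that the claims become narrower. The added BIS value shows the depth gap at the end MEP but cannot adjust it away.

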## **6. Study Design :**

**A comparative study will be used in this trial**

## **7. Ethical committee approval** (was it ethically approved by the department)

Yes

No

N/A

## **8. Study Methods**

### **Population of study & disease condition:**

40 Patients aged from 18-60 years old, scheduled for Cerebellopontine angle surgery will be included in the study. Patients will be randomly allocated using concealed closed envelope method into one of two groups: Induction will be accomplished with fentanyl, propofol, and a single dose of a neuromuscular blockade. Following intubation, general anesthesia was maintained with a continuous infusion of propofol and fentanyl.

Group A (n=20): will receive Rocronium as muscle relaxant, maintain partial NMB T2\TC 0.5 or TOF count 2 (10) and targeting BIS = (40-60)

Group B (n=20): will not receive muscle relaxant, targeting BIS = 25-35 after ending of monitoring of neurophysiology propofol dose will be dropped to 4–6 mg\kg\hr. targeting Bispectral index 40- 60.

### **Inclusion criteria:**

1. Patients age between >18 and<60.
2. Patients scheduled for neurosurgical CPA surgeries
3. Ability to sign the consent
4. ASA classification I, II

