**Possible Risk (mention if there is any risk or not):**

No possible risk.

**Primary outcomes** (Most important outcomes to be assessed)

1- End to start facial nerve MEP amplitude ratio.

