### **Sample size (number of participants included)**

We calculated our sample size using G-power software. Our primary outcome is end to start facial nerve MEP ratio was derived from a previous study to be mean  $0.72 \pm 0.43$  calculated by using previous results (12) with SPSS program. We assumed that ratio will decrease 50%. Considering a study power of 80% and a p-value of 0.05 to be significant, the sample size was calculated to be 38 patients (19 in each group). To compensate for drop-out we will recruit 20 patients in each group.

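### Lesion type is neither recorded nor used in a trial open to any CPA operation; this costs precision and makes a chance imbalance hard to interpret, but does not bias the comparison

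*Combined protocol and SAP*

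**What the plan says.** The only surgical entry criterion is "Patients scheduled for neurosurgical CPA surgeries" (section 8, Inclusion criteria). None of the exclusion criteria concerns pathology, lesion size, previous surgery or preoperative facial function.

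On allocation, section 8 (Population of study) says: "Patients will be randomly allocated using concealed closed envelope method into one of two groups". It mentions no strata, blocks or minimisation.

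The primary outcome is "End to start facial nerve MEP amplitude ratio". Methodology in details takes the first recording before skin incision and the second at dural closure.

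The Measurement tools list includes facial nerve function before and immediately after surgery, but not lesion type or size. Under Statistical analysis, two-group comparisons of quantitative variables use an unpaired t test, with no covariate.

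Section 4 (Background and Rationale) says: "Especially in cases of vestibular schwannoma excision, postoperative facial paresis and paralysis may occur despite efforts to avoid injury". It also notes that tumour bulk can hide the nerve from direct stimulation.

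**The concern.** The end-to-start ratio removes each patient's starting amplitude, but it spans the whole dissection. Any loss of facial nerve response caused by the resection therefore enters the primary outcome together with the effect of the assigned regimen. If schwannoma excision carries more of that loss, as the background suggests for facial palsy, lesion mix is a source of variance that the plan neither balances nor removes.

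Two things are at stake. The first is precision in a trial of 40. The second is whether the result can be read if the arms happen to differ in lesion mix: without the lesion fields, the report could neither show the imbalance nor adjust for it.

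**Working it through.** **Inputs from the documents.** Reference mean 0.72, SD 0.43, an assumed halving (difference 0.36), 80% power and a significance level of 0.05 with no sidedness given, 19 per arm calculated and 20 recruited (Sample size section).

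**Assumptions, not in the documents.** The share p of patients with a vestibular schwannoma: 50%, 75% or 90%. The gap D in mean ratio between lesion groups: 0.1 to 0.5. The SD of 0.43 is taken to apply in both arms and to include lesion variance.

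**1. The plan's own figure.** The standardised effect is 0.36/0.43 = 0.837. By the noncentral t, a one-sided test needs 19 per arm (power 81.2%), which matches the stated 38. A two-sided test needs 24 per arm. At 20 per arm, two-sided power is 73.2%, the baseline used below.

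**2. Chance imbalance.** With K of 40 patients having a schwannoma and 20 allocated to each arm, the number in Group A is hypergeometric(40, K, 20).

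- K = 20: a gap of 4 or more patients has probability 0.343; 6 or more, 0.113.
- K = 30: 0.273 and 0.065.
- K = 36: a gap of 4 or more, 0.106.

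**3. Shift caused by a 4-patient gap.** Shift = (4/20) × D. For D = 0.1 this is 0.02 (6% of 0.36); for D = 0.3, 0.06 (17%); for D = 0.5, 0.10 (28%). The unadjusted standard error is 0.43 × √(2/20) = 0.136, so each of these shifts is below one standard error.

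**4. Type I error.** In a simulation with K = 20, D = 0.36 and no treatment effect, the unadjusted t test rejects in 5.1% of all trials. It rejects in 8.2% of those with a gap of 4 or more patients, 13.4% of those with 6 or more, and 3.5% of those with 2 or fewer.

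**5. Power with a lesion factor in the model.** The variance share is R² = p(1−p)D²/0.43². The adjusted SE is 0.136 × √(1−R²), with 37 degrees of freedom. For example, p = 0.5 and D = 0.3 give R² = 0.25 × 0.09/0.1849 = 0.122 and SE = 0.127. With lesion type balanced between arms, two-sided power for 0.36 is:

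| Gap D | share 50% | share 75% | share 90% |
|---|---|---|---|
| 0.1 | 73.8% | 73.6% | 73.4% |
| 0.2 | 75.5% | 74.9% | 74.0% |
| 0.3 | 78.6% | 77.2% | 75.1% |
| 0.5 | 88.7% | 84.7% | 78.6% |

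**6. Adjustment without stratified envelopes.** Here the SE is divided by √(1−ρ²), where ρ is the correlation between arm and lesion type (at K = 20, a 4-patient gap gives ρ = 0.2). Averaged over the hypergeometric distribution at a 50% share, power is 72.6%, 74.4%, 77.5% and 87.8% for gaps of 0.1, 0.2, 0.3 and 0.5. Stratification therefore adds about 1 percentage point.

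**The case against.** Randomisation already deals with lesion mix. The unadjusted t test carries between-lesion variance in its SD, so its overall error rate is right. This stands. A reader might infer that the comparison is biased, or that an imbalanced trial would pass for an effect of relaxation. The documents do not support that: inflation appears only conditional on an imbalance and on an assumed lesion effect, and the shift is smaller than one standard error.

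The lesion effect is not in the documents. Nothing in them links lesion type to the MEP ratio itself, and a gap of 0.3–0.5 is about as large as the whole planned treatment effect. The larger gains also need a share near 50%, the most favourable value. This stands too, and it is why the full range is shown.

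The cited series for the SD is, by its title, on CPA surgery in general. If it was mixed, the heterogeneity is already in 0.43 and the sample size allows for it. A reader might blame the 73% baseline on lesion mix, but it comes from the sidedness of the calculation, which is a separate matter.

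Two limits concern the text. The absence of strata is read from silence; if strata exist, stating them settles that part. A reader might also count tumour bulk as a documented cause of nerve injury, but section 4 ties bulk only to access for direct stimulation. Only schwannoma is tied to palsy.

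Finally, preoperative facial function is already collected and could serve as a covariate. That is fair, but it does not replace knowing what lesion was operated on.

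**Conclusion.** The point holds as a matter of precision and interpretability, not validity. The plan opens entry to every CPA operation, names one lesion type as carrying particular risk of facial palsy, and then neither records nor uses lesion type. An imbalance of four or more patients between arms has a probability of 34% at a half share and 27% at 30 of 40.

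The benefit of correcting this ranges from negligible to useful. If lesion groups differ by 0.1–0.2 in mean ratio, two-sided power barely moves from 73.2%. At 0.3 it reaches 75.1–78.6%, and at 0.5 it reaches 78.6–88.7%, over shares of 90% down to 50%. Nearly all of this comes from adjustment. The share and the gap are both assumptions. The case for recording lesion type does not depend on either, because without it the baseline comparison cannot be reported.

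**What to change.** Keep the eligible population. Record lesion type (vestibular schwannoma or other) from the preoperative diagnosis, and largest diameter from the preoperative imaging. Prespecify a linear model for the primary ratio with arm and lesion type as factors, in place of the unadjusted t test. If envelopes are not yet prepared, make two sets in permuted blocks by the same factor, with the stratum fixed before the envelope is opened. With blocks of 4, the arms differ by at most 2 patients with a schwannoma.

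The cost is two case-report-form fields, one model term (one degree of freedom) and, if stratified, a second envelope set, with arm sizes that may drift from 20 by a patient or two. If lesion type is barely prognostic and allocation is not stratified, adjustment slightly lowers power (72.6% against 73.2% at a gap of 0.1 and a half share). No extra patients or procedures are needed.
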